**Resource Optimization in the Intensive Care Unit Setting: A Staff
Education and Scheduling Pilot Study to Improve Treatment
Decisions and Staff Satisfaction**

Study Protocol

Study ID: 20200060-01
Version Date: 05/29/2020

Project Title: Resource Optimization in the Intensive Care Unit Setting: A Staff Education and Scheduling Pilot Study to Improve Treatment Decisions and Staff Satisfaction

Principal Investigator: [name]

Co-Investigators [name], [name], [name], [name], [name], [name]

PART 1: INTRODUCTION

Intervention Description

This intervention pilot study has been developed for Intensive Care Unit (ICU) physicians and nurses by the Resource Optimization Network (RON) for implementation in The Ottawa Hospital (TOH) Civic Campus and the Montfort Hospital. The intervention targets ICU staff and is designed to reduce overall costs associated with ICU health care service delivery and improve staff satisfaction through reducing stress and associated burnout without sacrificing quality of care and patient outcomes. The intervention involves two components that (a) build ICU staffs' (i.e. physicians and nurses) knowledge to facilitate cost-effective and evidence-based decision-making about patient care (including tests, treatments, and procedures); and (b) optimize nurse scheduling to ensure the presence of the appropriate number of nurses per shift, thereby reducing stress, burnout and limiting the need for overtime. To evaluate the impact of the intervention, a pre/post-intervention design will be employed, with a 3-month pre-intervention period, followed by a 6-month intervention period and a 3-month post-intervention period.

Rationale for the Intervention

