Our research group (the RON) has studied a number of ICU interventions that have shown positive outcomes in terms of reducing costs while maintaining or even improving care. These include initiatives such as early palliative care involvement, early tracheostomy, and intensivists staffed NACU that once implemented, resulted in reduced ICU spending (8–10). In addition, Choosing Wisely Canada has launched a campaign to increase awareness around the appropriate use of clinical and treatment resources in critical care units by engaging and supporting health care professionals to take leadership in identifying and reducing unnecessary tests, treatments and procedures that are not supported by evidence and could harm patients (11). In terms of reducing burnout among staff, a systematic review investigating job satisfaction among critical care nurses found that shift worked and staffing were significantly correlated to critical care nurses' job satisfaction (12). Therefore, initiatives to optimize scheduling that effectively address staff burnout resulting from too much work with inadequate recovery are needed. We propose that the adoption of such programs in the ICU may result in savings of approximately one million dollars per year for both TOH and the Montfort Hospital.

The specific objectives of this intervention study are to:

1. Reduce ICU costs by reducing unnecessary ICU tests, treatments, and procedures and reducing the use of overtime
2. Improve staff satisfaction through reducing staff stress and burnout by optimizing staff scheduling

PART 2: DESCRIPTION OF INTERVENTION

Intervention Population

The intervention will target ICU staff, with one component geared generally for ICU staff (i.e. physicians and nurses) and one component geared specifically for ICU nurses.

Staff inclusion criteria: Employees who are a) aged 18 years or older; and b) providing direct patient care in the ICU at the Civic Campus of the Ottawa Hospital or the Montfort Hospital as a physician or nurse.

Recruitment

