In order to recruit ICU staff for participation in the educational workshops, a recruitment email invitation will be sent to all eligible ICU staff (i.e. physicians and nurses) and posters will be posted in staff breakrooms and high traffic zones (i.e. washrooms, ICU hallways). These recruitment invitations will explain to staff that participation in all intervention activities is voluntary and light refreshments will be provided. The email will also inform staff that the workshop will be held during a routine departmental meeting thereby maximizing convenience to promote participation.

Setting

This is a multicenter study. Study sites include the ICUs at two teaching hospitals in Ottawa: The Ottawa Hospital, Civic Campus and the Montfort Hospital.

Intervention Components

During an initial project meeting, the RON, a multidisciplinary team that includes experts in clinical ICU, analytics and scheduling, health economics and human factor engineering collaborating across various disciplines (nursing, pharmacy, physiotherapy, administration and management) evaluated the current status of the ICU service delivery, clinical outcomes and associated costs. Based on this, the team identified areas that could be easily modified while having a significant impact and designed relevant interventions to address areas best-suited to the ICUs at The Ottawa Hospital - Civic Campus and the Montfort Hospital (i.e., factoring in the culture of the ICU in their decisions).

There are two specific components that will be implemented concurrently over the 6-month intervention period, one targeted for ICU staff (i.e. physicians and nurses) and one targeted specifically for ICU nurses.

Component 1 – Educational Workshop: An educational workshop to increase ICU staffs' (i.e. physicians and nurses) awareness of the current Choosing Wisely Canada Critical Care strategies and recommendations to facilitate cost-effective and evidence-based decision-making about patient care (including tests, treatments, and procedures).

Component 2 - Optimizing Staff Scheduling: A strategy to optimize staff scheduling for ICU nurse (e.g. “staffing up” approach where more staff will be scheduled) in order to reduce overtime, absenteeism, stress and burnout of ICU nurses.

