We propose that the adoption of such programs in the ICU may result in savings of approximately one million dollars per year for both TOH and the Montfort Hospital. The two intervention components will be implemented with ICU staff members over the 6-month intervention period.

PART 3: EVALUATION PLAN

Goals of Evaluation

To evaluate the impact of this multicenter intervention, a pre/post-intervention design will be employed, with a 3-month pre-intervention period followed by a 6-month intervention period and a 3-month post-intervention evaluation period.

The evaluation will assess the extent to which the intervention achieves its' objectives. The results of the evaluation will help determine: (1) intervention effectiveness in reducing overall costs associated with ICU health care service delivery and reducing staff stress and burnout and (2) intervention feasibility.

We will evaluate the following study outcomes:

1. Primary outcomes: The primary outcomes of focus are ICU costs and ICU quality metrics.
2. Secondary outcomes: The secondary outcomes of focus are patient outcomes, ICU medical procedures, staff absenteeism, staff stress levels and burnout, and stakeholder perceptions.

Methods

Respondents

The evaluation will involve collecting data from intervention participants, namely ICU staff at the Ottawa Hospital Civic Campus and at the Montfort Hospital.

Staff inclusion criteria: Employees who are a) aged 18 years or older; and b) providing direct patient care in the ICU at the Civic Campus of the Ottawa Hospital or the Montfort Hospital as physicians, nurses, or allied health professionals (e.g., respiratory therapists, occupational therapists).

Stakeholder staff inclusion criteria: Employees who are a) aged 18 years or older; and b) whose roles provide them with direct knowledge of the ICU at the Civic Campus of the Ottawa Hospital or the Montfort Hospital and the interventions implemented during the study period (e.g., nurse managers, ICU managers, medical site lead).

Hospital administrative data, including patient data from all patients who are a) aged 18 years of older; and b) admitted to the ICU at the Civic Campus of the Ottawa Hospital or the Montfort Hospital during the 6-month study period will be collected to assess intervention effectiveness.

Sample Size

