Patient Data: Based on historical data from TOH, we conservatively estimate there will be 120 potentially eligible patients admitted to the ICU at the Civic Campus per month. We therefore anticipate that data will be collected from approximately 360 patients in the 3-month pre-intervention and 3-month post-intervention phases, respectively, and 720 patients during the 6-month intervention phase, equating to a total sample size of 1440 patients accrued over 12 months. At Montfort we estimate that the total sample size will be 500 patients over 12 months.

Of note, the data collected during the intervention period will not be included in the pre-post-intervention analyses. However, it will be used for quality assurance (i.e., stopping rules during interim analysis) and to further contextualize changes using run charts, as needed (e.g., of albumin use).

ICU Staff: Currently, there are approximately 194 staff members (i.e., intensivists, fellows, nurses, allied health professionals) providing direct patient care in the ICU at the Civic Campus and 50 staff members at Montfort. Based on previous research on survey and questionnaire response rates (13), we anticipate that at each time point (i.e., pre and post-intervention), 30% of ICU staff will complete the questionnaire, for a total sample size of approximately 58 respondents at TOH and 15 respondents at Montfort per time point.

ICU Stakeholder: We will aim to recruit between 5 to 10 relevant ICU stakeholder staff members at TOH and 3-5 staff members at Montfort (i.e., nurse managers, ICU managers, medical site

lead) for the post-intervention interviews. This sample size will ensure sufficient representation of stakeholder experiences, while bearing in mind the feasibility and time-involvement of qualitative data collection. These stakeholders will be purposefully sampled in order to ensure they are sufficiently information-rich (i.e., have knowledge of the ICU and the interventions that were implemented during the study) (14).

Recruitment

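### Overtime is part of Objective 1 but is not named as an outcome, and the nurse-only scheduling component has no nurse-only or role-adjusted analysis of stress, burnout or absenteeism

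*Combined protocol and SAP*

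**What the plan says.** **Overtime.** Objective 1, at the end of the Rationale in Part 1, is to "Reduce ICU costs by reducing unnecessary ICU tests, treatments, and procedures and reducing the use of overtime". The Intervention Description in Part 1 says that nurse scheduling will be optimised, "thereby reducing stress, burnout and limiting the need for overtime". Component 2 in Part 2 repeats the aim: "in order to reduce overtime, absenteeism, stress and burnout of ICU nurses". Goals of Evaluation in Part 3 then commits the study to checking its objectives: "The evaluation will assess the extent to which the intervention achieves" them.

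The primary outcomes are ICU costs and quality metrics. For the rest, "The secondary outcomes of focus are patient outcomes, ICU medical procedures, staff absenteeism, staff stress levels and burnout, and stakeholder perceptions". The measures to be drawn from the two hospitals' data systems (Quantitative Data) are costs, quality metrics, procedures and absenteeism. The cost items are total, direct, indirect and per-patient cost.

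**Nurses.** Objective 2 is to "Improve staff satisfaction through reducing staff stress and burnout by optimizing staff scheduling". On timing, "There are two specific components that will be implemented concurrently over the 6-month intervention period"; one is for physicians and nurses, the other for nurses alone. The survey population in Part 3 (Respondents, Sample Size, Questionnaire) includes physicians, nurses and allied health. Absenteeism is collected for full-time ICU staff. Role is a questionnaire item, and the questionnaire is anonymous. Data Analysis specifies t-tests and chi-squared tests, then regression on covariates found by comparing patient characteristics between periods.

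**The concern.** Objective 1 has two routes to savings. The first, fewer unnecessary tests and procedures, is measured directly through albumin use, ventilation, radiographs and transfusion. The second, less overtime, has no measure of its own. If costs change, the study cannot say whether overtime contributed. If costs do not change, it cannot say whether overtime fell and was offset, for instance by the extra scheduled hours that Component 2 envisages.

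For stress and burnout, the group whose scheduling changes is averaged with groups whose scheduling does not. A real change in nurses could be missed in the all-staff mean. Because the two survey waves cannot be linked person by person, a different mix of roles answering the second wave could also move that mean with no change in anyone's stress.

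**Working it through.** **1. Trace overtime through the plan.**

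| Place | Overtime named? |
|---|---|
| Intervention Description; Objective 1; Component 2 | Yes, as an aim |
| Primary and secondary outcomes | No |
| Measures taken from the data systems | No |
| Cost items | No; the plan does not say where nursing labour is booked |
| Data Analysis | No |

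**2. Trace role through the plan.** It is recorded in the questionnaire. Data Analysis contains no nurse-only analysis, no stratification by role and no role term, and its only named covariates are patient-level. No role field is stated for the absenteeism data.

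**3. Reproduce the plan's respondent numbers.** 0.30 × 194 = 58.2 (stated 58) and 0.30 × 50 = 15 (stated 15). Both agree. The plan gives no effect size, SD or power for any staff outcome, so there is no power figure to reproduce.

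**4. Illustrate the dilution.** From the plan: n = 58 per wave at The Ottawa Hospital and a 0.05 significance level. Assumed: two-sided tests, independent waves, a nurse effect d = 0.5 SD, no effect in other roles, no baseline difference between roles, and a nurse share f of 50-90%. The plan gives no nurse count. The upper end of the range allows for the Part 3 Recruitment text, which mentions only physicians and nurses as invitees.

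- All-staff: z = f·d·√(n/2)
- Nurse-only: z = d·√(f·n/2)
- Power = Φ(z − 1.96) + Φ(−z − 1.96)

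For f = 0.5, all-staff z = 0.5 × 0.5 × √29 = 1.346 and nurse-only z = 0.5 × √14.5 = 1.904.

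| f | Nurses per wave (58f) | All-staff power | Nurse-only power | Break-even g |
|---|---|---|---|---|
| 0.5 | 29.0 | 27% | 48% | 0.41 |
| 0.6 | 34.8 | 37% | 55% | 0.44 |
| 0.7 | 40.6 | 47% | 61% | 0.46 |
| 0.8 | 46.4 | 58% | 67% | 0.47 |
| 0.9 | 52.2 | 68% | 72% | 0.49 |

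**5. Break-even.** Suppose other roles gain a fraction g of the nurse effect. The all-staff z becomes d·[f + (1 − f)g]·√(n/2). It equals the nurse-only z when f + (1 − f)g = √f, so g = √f/(1 + √f). Above that value the all-staff test is the more powerful.

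**6. Precision of a nurse-only estimate.** The 95% half-width is 1.96·√(2/m). At The Ottawa Hospital, m = 29.0 to 52.2 gives 0.51 to 0.38 SD. At Montfort, 15 × 0.5 to 0.9 = 7.5 to 13.5 nurses gives 1.01 to 0.75 SD.

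**7. Role mix.** If the nurse share moved by 20 points between waves and roles differed by 0.5 SD (both assumed), the all-staff mean would shift by 0.20 × 0.5 = 0.10 SD with no true change. A role term addresses this. It does not undo the dilution, because a model with one common pre-post effect still averages over roles.

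**The case against.** The strongest reply is that the plan asks whole-intervention questions. Objective 2 speaks of staff, the components are concurrent by design, and no component-specific estimate is promised. That stands: the all-staff comparison is a correct analysis of Objective 2. A reader might infer that the nurse-only analysis should lead or be confirmatory. The documents do not support that. The objective is all-staff, the nurse-only advantage depends on an unknown nurse share and on little spillover to other roles, and neither analysis reaches 80% power at 0.5 SD anywhere in the range shown. Some spillover is plausible, since physicians also receive Component 1 and work in the same unit.

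On overtime, the reply is that it is worded as a route to lower cost and that cost is itself measured. That is fair as far as it goes: the primary cost outcome remains valid. A reader might infer that overtime is wholly outside the data. That is also too strong, since overtime pay may be inside total, direct or indirect costs. What survives is that Objective 1 names overtime, the evaluation promises to assess the objectives, and a cost total cannot show whether overtime fell. Stakeholder interviews may give impressions of overtime, but not hours.

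The regression wording could be read broadly enough to admit role. But the only covariates named are patient-level, and leaving role to be decided after the data are seen is not prespecification.

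**Conclusion.** Both omissions are real and follow from the text without any calculation. Followed as written, the plan could not report whether overtime fell, although that is a named part of Objective 1. It also has no stated way to look at stress, burnout or absenteeism in the group whose scheduling changes, or to guard the all-staff comparison against a shift in role mix.

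The size of the second problem is conditional. With the assumptions in the working, all-staff power is 27-68% against 48-72% nurse-only. The difference is about 21 points at a 50% nurse share (48 − 27) and about 5 points at 90% (72.4 − 67.8), and it reverses once other roles gain about 41-49% of the nurse effect. These figures apply to the stress and burnout scores, not to absenteeism. Confidence is high for the omissions and lower for the magnitude. The change is worth making before post-period data are seen, but the primary outcomes remain analysable without it. A nurse-only analysis should not be read as isolating Component 2, because nurses also receive Component 1.

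**What to change.** (a) Name nurse overtime hours, together with total paid nursing hours, as a secondary outcome at each site for the pre-intervention, intervention and post-intervention periods. Report them descriptively, for example on run charts. Sample Size already provides for these with patient data, "to further contextualize changes using run charts, as needed". Total paid hours are needed because overtime can fall while hours worked rise. State whether ICU costs include nursing wages and overtime pay, and under which cost item.

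(b) Keep the all-staff comparison of the Perceived Stress Scale and Maslach Burnout Inventory as the main analysis for Objective 2, adjusted for role. Prespecify a supportive nurse-only analysis of the same scores, with confidence intervals and labelled exploratory. Request role in the absenteeism extract and, if it is available, do the same there. Treat Montfort alone as descriptive.

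The cost is protocol wording and one more data extract per site. Access to overtime and paid-hours data must be confirmed, since the plan does not list them. The survey part needs no new data because role is already asked. The nurse-only sample is smaller (about 29 to 52 of 58 at The Ottawa Hospital under the assumed shares), and the added comparisons raise the chance of a false positive, which is why they should stay exploratory.

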ICU costs: Case costing will be used to determine the costs associated with ICU care during the study period, including: a) ICU total costs; b) ICU direct costs (i.e., all expenses to the hospital with fee codes linked to patient chart); c) ICU indirect costs (i.e., any overhead operational fees associated with service provided to patient); d) ICU cost/patient.

ICU Quality Metrics: The following outcomes will be included to evaluate the quality of ICU patient care during the study period: a) ventilator associated pneumonia; b) central line infections; c) C. difficile; d) number of patients receiving early mobilization

Patient outcomes: include a) length of stay (LOS); b) in-hospital mortality; c) patient and family satisfaction.

ICU medical procedures: Outcomes related to ICU medical procedures targeted in the educational intervention component will also be evaluated during the study period, including: a) albumin use; b) mechanical ventilation; c) chest radiographs; d) transfusion of red blood cells.

Staff absenteeism: We will collect data on ICU full-time staff absenteeism during the study period from the Data Warehouse and Montfort Archives.

2. Questionnaire: We will use an online questionnaire to evaluate ICU staffs' levels of stress and burnout. A self-administered online questionnaire taking approximately 15-20 minutes to complete will be used to obtain/assess pertinent demographic variables information (i.e., age, sex, ICU role [physician, resident, fellow; nursing; allied health]). Two instruments will be used to measure ICU staffs' level of perceived stress and job burnout.

The Perceived Stress Scale (PSS) (Appendix 1) (15) consists of 10 questions and is the most widely used psychological instrument for measuring perceptions of stress. The scale includes a number of direct questions to assess current levels of stress experienced and was designed to be non-content specific to any subpopulation.

The Maslach Burnout Inventory (MBI) (Appendix 1) (16) consists of 22 questions composed of three dimension that make up the construct of burnout: emotional exhaustion, depersonalization, and personal accomplishment. The MBI is the most widely used tool to measure burnout among professionals in the human services and has been validated in studies involving ICU nurses and physicians (5,6,17).

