The staff satisfaction questionnaire will be anonymous and no identifying information will be collected from participants. This multicenter study will be coordinated by the Principal Investigator. Data will not be transferred between institutions and no TOH PHI or PII will be shared externally with the Montfort Hospital.

Sign-up sheets circulated at the beginning of the Education workshop to collect participants information including name, title and email address will solely be for the purpose of sending the post-educational workshop survey. Sign-up sheets will be destroyed immediately after sending the follow-up emails.

iii. Data Analysis

Pre-post intervention analyses will be conducted to evaluate the outcomes of the intervention. Specifically, t-tests will be used to test for differences in continuous outcome measures, while

differences between categorical variables will be assessed using χ^2 tests. Chi squared tests and t-tests will also be used to compare patient characteristics in the pre and post intervention periods to examine potential covariates (e.g., patient demographics, comorbidity scores). Based on these sensitivity analyses, multivariate regression models will be run to adjust for covariates in the study outcomes. A p-value < .05 will be considered statistically significant.

Interim analysis will be performed 3-months after the intervention period begins. The results of this analysis will be presented to a Data Safety Monitoring Board.

Post-intervention interviews with ICU staff members will be digitally recorded and then transcribed verbatim. A thematic analysis will be performed wherein the qualitative data will be coded and categorized into larger themes describing stakeholders' satisfaction and perceptions of the intervention outcomes (19).

REFERENCES

1. Care in Canadian ICUs [Internet]. Canadian Institute for Health Information; 2016 Aug. Available from: https://secure.cihi.ca/free_products/ICU_Report_EN.pdf

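### Length of stay and ICU cost per patient are compared over all patients with no handling of death, and the separate mortality test is too imprecise to settle how a change should be read

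*Combined protocol and SAP*

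**What the plan says.** Under Goals of Evaluation (PART 3), "The primary outcomes of focus are ICU costs and ICU quality metrics", and "The secondary outcomes of focus are patient outcomes, ICU medical procedures, staff absenteeism, staff stress levels and burnout, and stakeholder perceptions". Under Data Collection, i. Tools, the cost outcomes end with "d) ICU cost/patient". The next groups include "Patient outcomes: include a) length of stay (LOS); b) in-hospital mortality; c) patient and family satisfaction". That section does not say whether length of stay means ICU or hospital stay.

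Under iii. Data Analysis, "t-tests will be used to test for differences in continuous outcome measures", and categorical outcomes are compared by chi-squared test, before versus after. Regression may then adjust for patient characteristics such as demographics and comorbidity. Neither section mentions death as a competing event, an analysis by survival status, or a rule for reading cost together with mortality.

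The stated aim (PART 1, Intervention Description) is to cut costs "without sacrificing quality of care and patient outcomes". No mortality margin is given. The first objective is "Reduce ICU costs by reducing unnecessary ICU tests, treatments, and procedures and reducing the use of overtime".

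**The concern.** A patient's ICU stay and ICU cost stop accruing at death. If extra deaths come sooner than the usual discharge, mean stay and mean cost fall although nothing has improved for anyone. If they come later, both rise. Adjustment for baseline characteristics does not remove this, because death happens after admission.

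The study's claim has two parts: lower cost, and no loss in patient outcomes. The plan tests the parts separately and gives no rule for combining them. A reported saving can then be taken at face value because the mortality test was not significant, although that test says little at this sample size.

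**Working it through.** **Inputs from the documents.** Civic Campus accrual is 120 patients a month. Montfort expects 500 over 12 months. An ICU day costs $4,186 (teaching-hospital average, Rationale). The hoped-for programme effect "may result in savings of approximately one million dollars per year for both TOH and the Montfort Hospital". The significance level is 0.05, taken here as two-sided.

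**Assumptions.** The documents give no baseline mortality, mean or SD of stay, or timing of deaths. All values for these below are assumed.

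**1. The plan's own figure.** 120 × 3 = 360 per three-month period, 120 × 6 = 720, and 360 + 720 + 360 = 1,440. This reproduces. The plan gives no power calculation to reproduce. Montfort adds 500 ÷ 4 = 125 per period if accrual is even, so 360 + 125 = 485 if the sites are pooled.

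**2. How small a shift matters.** If the $1 million is the combined figure, it is 1,000,000 ÷ (1,440 + 500) = $515 per patient, or 515 ÷ 4,186 = 0.123 ICU day. The shift in mean stay caused by deaths is (rise in mortality) × (days by which each added death shortens the stay). A 3-point rise gives 0.123 day if each death shortens the stay by 0.123 ÷ 0.03 = 4.1 days. At 2 days per death the rise needed is 6.2 points, and at 6 days it is 2.1 points. If the $1 million applies to each hospital, the shift doubles to 0.246 day. The 4.1 days is solved for, not observed. It shows the scale only.

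**3. Power of the mortality test.** Power = Φ[(d − 1.96·SE₀)/SE₁], where SE₀ uses the pooled proportion and SE₁ the separate ones. Example, 20% to 23% with 360 per period: SE₀ = √(2 × 0.215 × 0.785 ÷ 360) = 0.0306, SE₁ = 0.0306, and (0.03 − 0.0600) ÷ 0.0306 = −0.98, so power is 16%.

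| Assumed baseline, 3-point rise | 360 per period | 485 per period |
|---|---|---|
| 10% | 24% | 31% |
| 15% | 19% | 24% |
| 20% | 16% | 21% |

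**4. Precision.** The 95% half-width is 1.96 × √(2p(1−p)/n). At p = 0.20 it is ±5.8 points with 360 per period and ±5.0 with 485.

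**5. What the artefact does to the stay comparison.** Simulation: 4,000 trials, 360 per period, lognormal stays with coefficient of variation 1, survivors averaging 6 days in both periods, deaths averaging 2 days.

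| Mortality | Mean stay numerically shorter | Significantly shorter | Mortality significantly higher | Significantly shorter stay, mortality not significant |
|---|---|---|---|---|
| 20% to 20% | 51% | 2.6% | 3% | 2.3% |
| 20% to 25% | 69% | 7% | 36% | 2.7% |
| 20% to 30% | 83% | 16% | 88% | 0.7% |

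For the smaller 0.123-day shift with 485 per period, and an assumed SD of 4 to 10 days, a significantly shorter stay is expected in about 7% down to 4% of trials.

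**6. Direction.** With mortality going from 20% to 25%, deaths averaging 2 days lower mean stay by 0.2 day. Deaths averaging 6 days, as survivors do, leave it unchanged. Deaths averaging 10 days raise it by 0.2 day.

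**7. Whether another measure separates the cases.** In the 2-day example, mean stay goes from 0.80 × 6 + 0.20 × 2 = 5.2 to 0.75 × 6 + 0.25 × 2 = 5.0 days and looks better. Survivors stay at 6.0. ICU-free days over an illustrative 28 days, with deaths at 0, go from 0.80 × 22 = 17.6 to 0.75 × 22 = 16.5 and look worse, as they should.

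**The case against.** A reader might infer that a rise in deaths could be concealed and presented as a saving. The documents do not support that. In-hospital mortality stands in the same list as length of stay and would be tabulated and tested. An interim analysis goes to a Data Safety Monitoring Board. Stopping rules are mentioned under Sample Size, though not set out.

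Four further objections have weight:

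- The artefact would seldom produce a significant stay result alone (step 5), and a mortality rise large enough to do so more often would usually show in the mortality test. This stands. The effect is on the point estimate, which is what would be turned into a dollar saving.
- The direction cannot be known. No timing of deaths is given, and in-hospital deaths include those after ICU discharge, which do not shorten an ICU stay. This stands.
- Shorter stay is not a stated goal, and the savings are sought through fewer unnecessary interventions and less overtime. This is right for length of stay, but cost per patient is primary, with reduction as its aim, and has the same gap.
- All-patient cost is what the hospitals pay, so it is a legitimate primary measure. This stands. It argues against replacing the measure, not against supplementing it.

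The figure of 485 per period also needs pooled patient data and even Montfort accrual. The confidentiality section says data will not move between institutions, so 360 may be the relevant number. That would lower the power further.

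**Conclusion.** The gap is real and moderate. The plan lets a change in the rate or timing of deaths move both length of stay and a primary cost outcome, and it has no provision for reading them together with mortality. The mortality test has about 16–31% power for a 3-point rise from an assumed 10–20% baseline. Its interval is about ±5 to 6 points at 20% mortality. A non-significant result therefore leaves the second half of the study's claim open.

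The stronger conclusion, that the plan would turn excess deaths into an apparent success, does not follow. Mortality is reported alongside, the direction of the distortion is undocumented, and the distortion would rarely reach significance by itself. The figures rest on the assumed baseline mortality, stay lengths and spread. The 485 also rests on pooling and even accrual.

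**What to change.** In Data Collection (i. Tools) and iii. Data Analysis:

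- State whether length of stay is ICU or hospital stay.
- Keep all-patient length of stay and cost per patient as planned.
- Add one supporting analysis that does not reward death and uses the in-hospital data already collected. Either time to discharge alive with in-hospital death as a competing event, or ICU-free days over a stated horizon with in-hospital deaths set to 0, would serve.
- Tabulate length of stay and cost per patient by survival status, as description only. Survivors before and after may differ, because survival is itself an outcome, so this table should not decide whether a saving may be reported.
- Present any reduction in cost or stay beside the mortality difference and its 95% confidence interval.

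The cost is a few lines of text, one analysis and one table. No follow-up after discharge is needed. The drawback is that the added measure is less direct for managers than mean length of stay.
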